7.1.1.1.10 Echocardiogram

During Screening, an echocardiogram will be performed to evaluate the subject's left ventricular (LV) systolic function to ensure the subject's ejection fraction is $\geq 55\%$ ([Gebhard 2012](#)).

7.1.1.1.11 Biological Specimen Collection

Biological samples will be obtained, analyzed, and stored appropriately for future analysis. Blood will be drawn by a qualified medical provider, and urine specimens will also be collected. These samples may be used for re-testing, further evaluation of an AE and/or assessment, and follow-up of other exploratory endpoints. The timing and frequency for specimen collection and laboratory evaluations to be performed are described in the study's laboratory manual and in [Section 15 Schedule of Events](#).

Samples that remain after study testing is complete will be stored in the event additional testing (e.g., further evaluation of an AE or assessment of effect) is required. Samples will be stored in a deidentified coded form. Subjects (or their legally authorized representatives) can opt out of storage of samples for future analysis.

7.1.1.2 Procedures to Assess Safety

Subjects enrolled in the trial will be monitored closely to assess safety and tolerability of the study agent and intervention. Study-specific procedures that will be used for this purpose are summarized below.

Information regarding the timing and frequency of these procedures is provided in [Section 7.3 Study Schedule](#).

- Review of AEs
- Review of medications
- Vital signs
- 12-Lead ECGs
- Targeted physical exams
- Weight
- End of Study (or Early Termination) physical examination
- Blood and urine collection for clinical laboratory evaluations

7.1.1.2.1 Review of Adverse Events

AEs will be reviewed, documented, and reported as required at each visit (from time of consent through End of Study). For definitions, guidance, and additional information regarding AEs, refer to [Section 8](#).

7.1.1.2.2 Review of Medications

The investigator or designee should review the subject's current medications, including over-the-counter drugs, herbal supplements and/or vitamins, as well as those taken by the subject since the last visit. Changes to the subject's list of medications should be reviewed and recorded. Review of medications should occur at every visit.

7.1.1.2.3 Vital Signs

Refer to [Section 7.1.1.1.7](#) for a description of vital signs. Vital signs will be collected at every visit. During infusions, vital signs will be collected according to the Infusion Administration Manual by the blinded Outcomes Assessor.

7.1.1.2.4 12-Lead ECG

Refer to [Section 7.1.1.9](#) for information pertaining to 12-Lead ECGs.

7.1.1.2.5 Targeted Physical Exams

During the dosing period, a targeted physical exam, including auscultation of the heart and lungs, an assessment of peripheral edema, and weight, will be performed per the Study Schedule ([Section 7.3](#)).

7.1.1.2.6 Physical Examination

Refer to [Section 7.1.1.8](#) for a description of the complete physical exam. The complete physical exam will be performed at Screening and repeated at End of Study (or Early Termination).

7.1.1.2.7 Blood and Urine Collection for Laboratory Evaluations

As described in [Section 7.1.1.11](#), subjects will have blood and urine samples collected for clinical

evaluation ([Section 7.2.1 Clinical Laboratory Evaluations](#)). Refer to [Section 15 Schedule of Events](#) for timing and frequency of blood and urine collection for laboratory evaluations.

7.1.1.3 Procedures to Assess Efficacy

Cognitive function will be assessed using assessment scales administered by qualified raters. Raters must be certified, as appropriate. The same rater should be used for the duration of each subject's participation unless a change in rater is unavoidable. Additionally, for scales that require an informant (e.g., caregiver), the informant should be consistent throughout the duration of each subject's participation unless a change is unavoidable. Informants must have frequent contact with the subject (defined as approximately 10 hours per week). The following scales will be used during the course of this study:

- MMSE
- SIB
- ADCS-ADL-Severe
- ADCS-CGIC
- NPI or NPI-NH

Information regarding the timing and frequency of these procedures is provided in [7.3 Study Schedule](#).

7.1.1.3.1 Mini-Mental Status Examination

Refer to [Section 7.1.1.1.2](#) for information pertaining to the MMSE.

7.1.1.3.2 Severe Impairment Battery

The SIB is designed to assess cognitive abilities in patients with severe AD. The SIB is divided into scorable subscales that cover orientation to time and place, attention, language, praxis, visuospatial ability, construction, memory, orientation to name, and social interaction. Scoring gives credit to nonverbal and partially correct answers, thus decreasing the need for language output. There are 57 items, and it takes approximately 20 minutes to complete. The range of possible scores is 0-133 ([Panisset 1994](#), [Appendix 2](#)).

7.1.1.3.3 Alzheimer's Disease Cooperative Study Group Activities of Daily Living Inventory for Severe Alzheimer's Disease

The ADCS-ADL-Severe assesses the competence of patients with AD in performing basic activities of daily living. The ADCS-ADL-Severe contains 19 items covering physical and mental functioning and independence in self-care (e.g. dressing, grooming, bathing, eating, walking, and toileting). For each ADL, an informant (e.g., caregiver) is first asked if the patient attempted the activity during the past 4 weeks. If a patient did attempt the ADL, the informant is asked to choose the single most accurate definition of the patient's level of performance. The scores range from 0 to 54, with higher scores indicating less functional impairment ([Galasko 2005](#), [Appendix 3](#)).

7.1.1.3.4 Alzheimer's Disease Cooperative Study – Clinical Global Impression of Change Caregiver Input

The ADCS-CGIC is a systematic method for assessing clinically significant change in a clinical trial as viewed by an independent skilled and experienced clinician. The ADCS-CGIC focuses on clinicians' observations of change in the subject's cognitive, functional, and behavioral performance since the beginning of a trial. It relies on both direct examination of the subject and interview of informants ([Ferris 1997](#), [Schneider 1997](#), [Appendix 4](#)).

7.1.1.3.5 Neuropsychiatric Inventory or Neuropsychiatric Inventory – Nursing Home Version

The NPI ([Cummings 1994](#)) comprises 10 behavioral areas and 2 types of neurovegetative changes (12 domains): delusions, hallucinations, agitation/aggression, depression/dysphoria, anxiety, elation/euphoria, apathy/indifference, disinhibition, irritability/lability, aberrant motor behavior, sleep and nighttime behavior disorders, and appetite/eating changes. Information is gathered from caregivers familiar with the patient's behavior. To serve as an informant, the caregiver must have at least daily contact with the patient. Initial responses to each domain screening question are "Yes" (present) or "No" (absent). If the response to the domain question is "No," the interviewer goes to the next question. If "Yes," the interviewer proceeds to ask the informant a series of subquestions for that domain. For each behavioral domain, there are 4 scores: frequency, severity, domain total score (frequency x severity), and occupational disruptiveness. Thus, the NPI evaluates response to therapy and provides symptom severity and distress ratings for each symptom reported, as well as total severity and distress scores reflecting the sum of individual domain scores.

The NPI-NH was derived from the NPI ([Cummings 1994](#)) to evaluate the neuropsychiatric manifestations and psychopathology of patients with AD and other dementias who reside in nursing homes, extended care facilities, or other long-term care settings. The NPI-NH is an interview-based scale designed to be administered to an informed professional nursing home caregiver (as opposed to a family or home-based caregiver in the standard NPI) involved in the daily care of the subject. Generally, the NPI-NH is used to evaluate changes in subject behavior that have appeared during a given period ([Wood 2000](#), [Appendix 5](#)).

7.2 LABORATORY PROCEDURES/EVALUATIONS

7.2.1 CLINICAL LABORATORY EVALUATIONS

Biological samples (e.g. whole blood, serum, urine, buccal swab) will be collected for laboratory evaluations in accordance with the Schedule of Events ([Section 15](#)). Clinical sample processing and laboratory evaluations will be conducted by certified Clinical Laboratory Improvement Amendments (CLIA) facilities. Refer to the study's laboratory manual for complete information regarding all laboratory evaluations to be performed, sample collection procedures, and related requirements.

The investigator is responsible for determining and documenting if out of range laboratory values are clinically significant or not. All clinically significant values will be recorded as AEs in the CRF and followed until resolution, unless the subject is lost to follow up. Once resolved, the appropriate CRF page(s) will be updated.

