8.1 SPECIFICATION OF SAFETY PARAMETERS

8.1.1 DEFINITION OF ADVERSE EVENTS (AE)

Per 21 CFR 312.32(a) an AE is any untoward (unfavorable, harmful, or pathologic) medical occurrence in a subject administered a medicinal (investigational) product even if the event does not necessarily have a causal relationship with this treatment.

An AE can therefore be any unfavorable and unintended sign (including an abnormal laboratory finding that is deemed clinically significant), symptom, or disease temporally associated with the use of a medicinal

(investigational) product whether or not related to the medicinal (investigational) product.

An AE does include any:

- Exacerbation of a pre-existing illness.
- Subjective or objective symptoms spontaneously offered by the subject or the subject's caregiver and/or observed by the investigator or study staff.
- Increase in frequency or intensity of a pre-existing episodic event or condition.
- Condition detected or diagnosed after study drug administration even though it may have been present prior to the start of the study (unless it can be demonstrated by medical record review that the onset of the event preceded the date/time of Informed Consent).
- Continuous persistent disease or symptoms present at baseline that worsen following the start of the study.
- Symptoms associated with disease not previously reported by the subject/caregiver.
- Untoward medical occurrences considered by the investigator to be related to study-mandated procedures.
- Abnormal assessments (e.g., change on physical examination, ECG findings), if they represent a clinically significant finding, that were not present at baseline or worsened during the course of the study.
- Laboratory test abnormalities, if they represent a clinically significant finding, symptomatic or not, which were not present at baseline or worsened during the course of the study.

An AE DOES NOT include a/an:

- Elective medical or surgical procedure (e.g., surgery, endoscopy, tooth extraction, transfusion).
- Pre-existing diseases or conditions present or detected at the start of the study that do not worsen.
- Situations where an untoward medical occurrence has not occurred (e.g., hospitalization for cosmetic elective surgery, social and/or convenience admissions).
- The disease or disorder being studied or sign or symptom associated with the disease or disorder unless more severe than expected for the subject's condition.

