8.4 REPORTING PROCEDURES

8.4.1 ADVERSE EVENT REPORTING

All subjects who have given informed consent will be evaluated for AEs. All AEs that occur after the time of treatment with the study agent will be considered Treatment Emergent AEs. Subjects with Treatment-Emergent AEs must be followed until the AE is resolved or is stable, unless the subject is lost to follow up.

Each AE or suspected adverse reaction must be described as follows: the date of onset, date of resolution, severity (mild, moderate, severe), frequency of the event (single episode, intermittent, continuous), action taken with study treatment (no action taken, treatment held, treatment discontinued), outcome, causality* (unrelated, possibly related, definitely related), and seriousness criteria. Each AE or suspected adverse reaction must be recorded separately.

***Note:** Causality assessment will be made only when the AE occurs after the subject has initiated at least one infusion of the study agent. An AE occurring before the subject's exposure to study agent will always be labeled as "unrelated".

Any AE occurring during the study must be documented in the subject's medical records and as an AE in the CRF. Any SAE occurring during the study must be documented in the subject's medical records and as an SAE in the CRF.

A separate set of SAE pages should be used for each SAE. However, if at the time of initial reporting,

multiple SAEs are present that are temporally and/or clinically related, they may be reported on the same SAE page.

The investigator should attempt to establish a diagnosis of the event (that meets the definition of an AE or SAE) based on signs, symptoms, and/or other clinical information. In such cases, the diagnosis should be documented as the AE and/or SAE and not the individual signs or symptoms. The diagnosis will become the basis for the verbatim term as reported by the investigator. If no diagnosis is known, and clinical signs and symptoms are not present, the abnormal finding should be recorded.

In addition to the investigator's own description of the AEs, each AE will be encoded according to the MedDRA.

The investigator will take all appropriate and necessary therapeutic measures required for resolution of the AE. Any medication necessary for the treatment of an AE must be recorded on the concomitant medication CRF.

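### Protocol 7.2.1 records every clinically significant lab value as an AE, without the limits in 8.1.1 and 8.4.1, so one diagnosed event can fill several rows of the primary AE tables

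*Protocol*

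**What the plan says.** Protocol 7.2.1 leaves the judgment of clinical significance to the investigator and continues: "All clinically significant values will be recorded as AEs in the CRF and followed until resolution, unless the subject is lost to follow up". It attaches no baseline condition and no diagnosis condition, and it does not refer to Section 8.

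Protocol 8.1.1 addresses lab results in three places:
- The general definition counts as an AE "any unfavorable and unintended sign (including an abnormal laboratory finding that is deemed clinically significant"), with no condition that the finding be new or worse.
- The list of what an AE includes has clinically significant lab results, "symptomatic or not, which were not present at baseline or worsened during the course of the study".
- The list of what an AE does not include has "Pre-existing diseases or conditions present or detected at the start of the study that do not worsen".

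Protocol 8.4.1 tells the investigator to try to establish a diagnosis, and then: "In such cases, the diagnosis should be documented as the AE and/or SAE and not the individual signs or symptoms". The abnormal finding itself is recorded when there is neither a known diagnosis nor clinical signs and symptoms.

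The primary safety endpoint (Protocol 4.2.1) is the incidence of treatment-emergent AEs and SAEs by MedDRA PT, grouped by SOC. Protocol 8.4.1 treats an AE as treatment-emergent if it occurs after treatment. SAP 6.1.2 uses whether it was reported, or worsened, on or after the start of dosing. The SAP does not reconcile the recording rules.

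**The concern.** For a diagnosed event with abnormal labs, a site cannot satisfy both 7.2.1 and 8.4.1. The first asks for an AE for each clinically significant value. The second asks for the diagnosis in place of its signs, and 8.1.1 itself classes a clinically significant lab finding as a sign.

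The rows at stake are the PT rows, and possibly SOC rows, that make up the primary endpoint. In a trial of about 20 subjects, those rows are the main safety result. Their lab-related content should not depend on which section a site happened to follow.

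**Working it through.** **1. The rules side by side**

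| Lab result, judged clinically significant | 7.2.1 | 8.1.1 lab bullet | 8.4.1 |
|---|---|---|---|
| New; no diagnosis, no clinical signs or symptoms | AE | AE | Record the finding |
| New; part of a diagnosis | AE | AE | Record the diagnosis, not its signs |
| Present at baseline, unchanged | AE | Not covered | No specific rule |

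The sections agree in the first row and diverge in the other two.

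**2. Main route: a diagnosis plus its lab values**

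Take a renal event as an example. Reduced kidney function is an AE of special interest (Protocol 8.4.3). Creatinine, BUN, potassium and TCO2 are all drawn at Visits 4, 5, 6, 8, 9 and 10 (Protocol 15.1, notes e to g).

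- Under 8.4.1: 1 diagnosis = 1 recorded event.
- Under 7.2.1 read literally, if all four values are judged clinically significant: 1 diagnosis + 4 values = up to 5 recorded events.

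Protocol 10.4.2 counts repeat reports of the same AE in a subject once, and SAP 6.1.4 counts subjects with at least one occurrence of each event. Neither merges a diagnosis with a lab value coded to a different term. Exclusion 17 does not help, because these values are new after dosing. The any-TEAE row (SAP Table 14.3.1.1) counts the subject once either way, provided the diagnosis is a TEAE.

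**3. Secondary route: an unchanged value first recorded after dosing**

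Exclusion 17 (Protocol 5.2) bars clinically significant abnormalities in the blood count, metabolic panel, albumin, coagulation tests, three vitamins and TSH. It does not name iron, magnesium, phosphate, CPK or LDH. All five are tested at Screening and again at Visits 8 and 9 (Protocol 15.1, notes c and f). If such a value is clinically significant and unchanged, but first written up as an AE after dosing, the word reported in SAP 6.1.2 can make it a TEAE. The word occur in Protocol 8.4.1 points the other way.

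**4. Weight of one subject**

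The only sample-size arithmetic visible in the plan reproduces and is not in dispute: 20 × (1 − 0.20) = 16 evaluable.

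Arm sizes are derived from about 20 subjects at 2:1: 20 × 2/3 = 13.3, taken as 13, and 20 × 1/3 = 6.7, taken as 7.

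- GRF6019 row: 1/13 = 7.7 percentage points.
- Placebo row: 1/7 = 14.3 percentage points.
- With a 14/6 split: 1/14 = 7.1 and 1/6 = 16.7 points.

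**5. How often**

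The documents give no rate. If each subject has an assumed chance p of at least one such extra lab AE, the chance of at least one affected subject among 20 is 1 − (1 − p)^20:

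- p = 2%: 33%
- p = 5%: 64%
- p = 10%: 88%
- p = 20%: 99%

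The width of this range shows that frequency cannot be settled from the documents.

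**The case against.** The strongest reply is that the protocol already says which section governs. Section 7.1.1.2.1 sends the reader to Section 8 for AE definitions and guidance. On that view, 7.2.1 only says who judges significance and where the result is entered, and it never says in terms that a value must be recorded in addition to its diagnosis. This has some force, and many sites would read it that way. But the pointer is a general one, and 7.2.1 says all clinically significant values with no exception, so the literal reading remains open.

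Several stronger readings are tempting, and the documents do not support them:

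- *That 8.1.1 admits only new or worsened lab values.* Its lab bullet has that condition, and the exclusion of unchanged pre-existing conditions supports it. The general definition in the same section is broader.
- *That unchanged Screening abnormalities will commonly enter the TEAE tables.* AEs are collected from consent. A site applying 7.2.1 at Screening would record the value then, and Protocol 10.4.2 tabulates pre-dose AEs separately. The value has to be missed, or recorded afresh, after dosing. Exclusion 17 removes the main panels, and exclusion 23 gives the investigator further discretion.
- *That repeated reports of one abnormality pile up.* They count once.
- *That recording habits bias the comparison between arms.* AEs are assessed by blinded staff, so recording should not depend on allocation. Randomization is stratified by sex and not by site, so chance imbalance is possible, but nothing in the documents sizes it.
- *That five recorded events necessarily become five PTs over several SOCs.* That depends on MedDRA coding that the documents do not contain.

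**Conclusion.** The inconsistency is real and should be corrected. Read literally, 7.2.1 lets one diagnosed event occupy the diagnosis row and one or more lab rows of the primary PT/SOC tables, and no counting rule in either document removes the extra rows. The unchanged-value route exists but is narrow.

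The size is illustrative: about 7.7 points per extra subject in a GRF6019 row and 14.3 in a placebo row, assuming arms of 13 and 7. These are simply 1/n and would apply to any single event. No frequency can be derived from the documents.

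A reader might infer that the overall TEAE incidence, the sample size or an error rate is compromised. None of these follows. The any-TEAE row does not move when the diagnosis is itself a TEAE, the sample-size arithmetic is untouched, and SAP 6.1.4 plans no formal AE testing unless indicated otherwise. This is a wording conflict with a modest effect on the primary tables and a cheap remedy.

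**What to change.** Change the 7.2.1 sentence to: *Clinically significant values that meet the AE definition in 8.1.1 (not present at baseline or worsened), and that are not part of a diagnosis recorded under 8.4.1, will be recorded as AEs.* Carry the same rule into the CRF guidance.

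In SAP 6.1.2, define a TEAE by onset or worsening on or after the first dose, in place of reporting. This closes the secondary route and agrees with Protocol 8.4.1.

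The follow-up wording also differs. Section 7.2.1 follows a value until it resolves, while 8.4.1 allows follow-up to end at resolution or stability and covers only treatment-emergent AEs. The sponsor must reconcile the two, including for values arising between consent and first dose. No follow-up rule is proposed here.

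The cost is a small protocol amendment, which needs IRB approval before use (Protocol 12.2), a one-line SAP change and a site memo. Collected values remain in the listings (SAP Section 2), so no data are lost. Not every test has a named summary table, however: SAP 6.2 covers hematology, serum chemistry and urinalysis, so coagulation results may appear only in Listing 16.2.8.1.

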7.2.2 OTHER ASSAYS OR PROCEDURES

7.2.2.1 Apolipoprotein E (ApoE) Genotype Testing

ApoE genotype is a known risk factor for AD pathogenesis, with presence of the ApoE ε4 allele carrying increased risk. This risk is further influenced by age, sex, race, and ethnicity. Thus, determining ApoE genotype at Baseline will allow for the assessment of possible differential effects of ApoE genotype on safety, treatment efficacy, and other exploratory measures.

7.2.2.2 Proteomic and Genetic Biobanking

Blood and plasma will be collected from subjects at multiple timepoints throughout the trial for biobanking. For information regarding the timing and procedures for sample collection and related requirements, refer to

the study's laboratory manual and [Section 15 Schedule of Events](#).

Plasma will be analyzed by proteomics using mass spectrometry and targeted approaches to assess the specific signature of proteins in subjects at Baseline and to assess the changes in the proteome with repeated GRF6019 infusions. These methodologies will provide a broad overview of the proteins that are present in the plasma sample by assessing 1000-5000 analytes and allow generation of a proteomic signature. From this signature, we hope to identify key proteins that are drivers of cognitive function and/or indicators of disease progression. Blood samples will be retained for analysis of emergent genetic markers of disease. By understanding the composition and function of plasma samples from the trial, we seek to identify the biomarkers relevant to further optimizing treatment in AD. For information regarding future use of stored samples, see [Section 12.5 Future Use of Stored Specimens](#).

